**Fit and Strong! Plus Comparative Effectiveness Trial**

**NCT03180008**

**Trial protocol and analysis plan**

**7/22/2016**

## **SIGNIFICANCE (All revisions are in bold and *italics*.)**

Osteoarthritis (OA) is the most common condition affecting older adults and the principal cause of disability among them (Hootman et al., 2009). Previously, we demonstrated that lower extremity (LE) joint impairment caused by OA is the route through which disability develops (Dunlop, [name] et al., 1998). Importantly, LE symptomatology related to OA can be caused or exacerbated by obesity. Longitudinal data show that a 5.1 kg weight loss over 10 years decreased the odds of developing knee OA by more than 50% (Felson et al., 1992). Obesity also exacerbates OA pain and disability (Hartz et al., 1986). Cross-sectional data from population-based studies show strong associations between moderate overweight and self-reported OA of the hip or knee (OR = 1.7), chronic LE pain (OR = 1.6) and mobility disability (OR = 1.7) (Tukker, Visscher, and Picavet, 2009) as well as associations between foot OA, obesity, and impaired functional performance on chair stand and 8-foot walk times (Golightly et al., 2011).

The prevalence of obesity (BMI  $\geq 30$ ) among older adults has increased rapidly in the U.S. For example, the prevalence of obesity among people aged 60-69 increased 56% between 1992 and 2002 (Villareal et al., 2005). By 2007-8, 37.1% of men and 48.1% of women 60 or older were obese. (Flegal et al., 2010) **Despite this increase, a recent meta-analysis reports a lack of high quality evidence to support the efficacy of weight loss programs in older adults (Witham and Avenell, 2010). Nationally, obesity prevalence in 2009 was 54% higher among adults with arthritis than among those without the condition, and the number of states with prevalence  $> 30\%$  increased from 38 in 2003 to 48 (Hootman et al., 2011a). Recent CDC data indicate that arthritis affects 35.6% of persons with obesity. Importantly, persons who were obese and had arthritis were 44% more likely to be physically inactive compared to persons who were obese without arthritis (Hootman et al., 2011b).**

The relationship between obesity and LE OA in part explains recent rapid increases in hip and knee replacement surgery in the U.S. In 2004, 225,900 hip and 431,485 knee replacements were performed, representing increases of 37% and 53%, respectively, since 2000 (Kim, 2008). Hospital costs for these procedures in 2004 were \$11 billion and nearly 600,000 hip and 1.4 million knee replacements are projected to be performed in 2015 (Wilson et al., 2008). **Finally, simulations of the impact of obesity and knee OA on morbidity and mortality of older Americans estimate that total losses of per-person quality-adjusted life years range from 1.9 in non-obese persons with OA to 3.5 for persons affected by both conditions, resulting in 86.0 million quality-adjusted life-years lost to obesity, knee OA, or both, with disproportionately high losses seen among Hispanic and black women. Reversing obesity levels to those seen 10 years ago would avert 111,206 total knee replacements (Losina et al. 2011).** Together, this body of evidence indicates an urgent need for the testing and rapid translation of evidence-based public health interventions that can reverse or mitigate obesity among older adults with OA.

Completed Work. Fit and Strong! is an evidence-based physical activity (PA)/behavior-change program that effectively addresses symptoms experienced by older adults with LE OA ([name] et al., 2004; [name] et al., 2006). Previous research has shown that older adults with OA have strength and aerobic deficits compared to age matched controls (Fisher et al., 1991; Minor et al., 1989). The pain and stiffness older adults with OA experience in weight bearing LE joints leads to and/or exacerbates sedentary behavior in this population. Sedentary behavior, in turn, leads to muscle wasting and decreased aerobic capacity. Fit and Strong! was designed to address and reverse these deficits. Fit and Strong! is a group- and facility-based program that meets 90 minutes, 3 times per week for 8 weeks (24 sessions total). The first 60 minutes focus on multiple-component exercise including flexibility/balance, aerobics, and LE strengthening using exercise bands and adjustable ankle cuff weights. Instructors progressively challenge participants' balance during exercise. The remaining 30 minutes are devoted to group problem solving and education using a Social Cognitive Theory (SCT)-based curriculum that facilitates arthritis symptom management and promotes self-efficacy (SE) for exercise and adherence to exercise over time. In Week 6, participants meet with instructors to *negotiate* an *individualized* PA maintenance plan with the goal of maintaining 20 minutes of flexibility, aerobic, and strength exercise 3 or more times per week.

Efficacy. We tested the *efficacy* of Fit and Strong! in an RCT with 215 individuals with OA ([name] et al., 2004; [name] et al., 2006). Relative to controls, treatment participants improved significantly in SE for exercise, exercise participation, and LE stiffness after 8 weeks. At 6 months, participants retained the original gains and had significant benefits vs. controls in SE for exercise adherence, LE pain, and SE for arthritis pain management. At 12 months, significant effects were maintained on SE for exercise and exercise participation,

accompanied by marginally significant reductions in LE stiffness and pain. Effect sizes were 0.798 and 0.713 for SE for exercise at 6 and 12 months, respectively, and 0.905 and 0.669 for exercise participation in the treatment group.

The exercise component of Fit and Strong! was originally designed and taught by licensed physical therapists but is now taught by certified exercise instructors (CEIs) to expand its reach (Glasgow, Vogt, and Boles, 1999). At 2 and 6 months participants under both instruction modes improved significantly over baseline with respect to LE pain, stiffness, physical function, LE strength (timed-stand), and aerobic capacity (6 minute distance walk) (Seymour, [name] et al., 2009). Participants rated both types of instruction highly, attendance was identical, and no adverse health effects were reported.

**Effectiveness.** Our recent effectiveness trial (N=486) compared two ways of reinforcing maintenance of PA after the 8 week program ends. We compared maintenance outcomes for participants with a customary Fit and Strong! negotiated maintenance plan to participants who were mainstreamed to an existing PA program at the same facility. We examined the effectiveness of both approaches with and without tapered telephone reinforcement (TR) (NIA R01 AG23424). Findings showed that persons in the *negotiated TR group* showed the greatest amount of PA maintenance at 18 months, followed by the *customary negotiated follow-up group* ([name] et al., 2010). *Across all four study arms, we found significantly increased maintenance of PA at 18 months as well as significantly improved LE stiffness, pain, and function; LE strength (sit-stand); 6-minute distance walk; and anxiety and depression ([name] et al., 2010). The impact on gait speed is notable given recent findings that gait speed, along with age and sex, is a strong predictor of survival (Studenski et al., 2011).*

**Translation.** We are currently funded by CDC (R18 DP001140) to translate Fit and Strong! in collaboration with Area Agencies on Aging in Illinois and North Carolina. Both CDC and AoA have recommended Fit and Strong! as an evidence-based program that all states should promote. We also provide the program in Florida in collaboration with the Health Foundation of South Florida and the Florida Department of Elder Affairs. Single group pre-post findings from a reduced set of outcomes obtained on the first 272 participants in this effort show a continued statistically significant impact on LE pain and stiffness, energy/fatigue, and SE for exercise at two months accompanied by a *marginally significant impact on BMI*, demonstrating consistent benefits of the program on important outcomes. However, *the current program does not explicitly address the relationship between weight and presence/exacerbation of LE OA symptomatology, nor does it address changes in diet for sustained weight loss over time.*

**To date, two studies have shown that combining PA with weight loss is more effective than either approach alone in improving the functioning of older adults. Rejeski et al. (2011) found that a combined PA/reduced caloric intake intervention with older adults with cardiovascular disease achieved an 8% weight loss at 6 months that was maintained at 18 months, accompanied by improved mobility. Using a similar approach with a general population of older adults, Villareal and colleagues found a 9% decrease in weight at 12 months that was accompanied by a 21% increase on the physical performance test (Villareal et al., 2011). Importantly, to date, only one study (ADAPT) has tested the impact of combined PA/weight reduction on older adults with OA.** The ADAPT trial randomly assigned 316 sedentary persons 60 years of age and older with knee OA and BMI > 28 kg/m^2 to one of four 18-month interventions: dietary weight loss, exercise, dietary weight loss + exercise, or control (Messier et al., 2004). The ADAPT PA intervention was very similar to Fit and Strong!, using a 24-week intensive *facility-based program* that met 3 times per week for 60 minutes. Exercises included flexibility, aerobics, and resistance training. At 4 months, participants transitioned to a home-based program accompanied by TR. The weight control intervention sought to achieve an average weight loss of 5% over 18 months through a 4-month intensive phase (16 weekly sessions), a 2-month transition phase (bi-weekly sessions), and a 12-month maintenance phase (monthly sessions plus TR). The intervention focused on lowering caloric intake by improving self-regulatory skills.

The combined PA/diet group showed the strongest effects, including significant improvement in LE physical function (WOMAC), 6-minute distance walk, stair-climb time, and knee pain, as well as a 5.7% weight loss. These findings indicate that a *combination of modest weight loss plus moderate exercise provides better pain and mobility outcomes for obese adults with knee OA than weight loss or PA alone* (Messier et al., 2004). In a more recent study that included a weight loss component based on meal replacement, nutrition education, and lifestyle behavior modifications, Messier and colleagues found a weight reduction of 8.7% at six months (Messier et al., 2009). However, meal replacement is probably not scalable as a public health strategy for

diverse populations (Miller et al., 2006). The importance of findings from both Messier studies is reinforced by a recent meta-analysis which demonstrated that *physical disability among overweight persons with knee OA diminishes after a moderate weight loss (5%) and indicated that this level of weight loss is achievable within 20 weeks* (Christensen et al., 2007).

## INNOVATION

*Despite the urgent need for interventions that target overweight/obese older adults, a recent meta-analysis found a striking lack of evidence supporting the effectiveness of weight loss interventions for this population (Witham and Avenell, 2010). Interventions that combined PA and diet had the best results with respect to weight reduction. However, of 9 studies examined, only 2 combined PA with diet. One was ADAPT (reviewed above) and the other examined outcomes only to 12 months (Villareal et al., 2008). To date, ADAPT is the only trial that has demonstrated that it is possible to reduce caloric intake among older adults with OA, resulting in a 5.7% weight loss. However, ADAPT was conducted in clinical settings with limited scalability. The subsequent IDEA trial achieved an 8.7% weight loss at 6 months but used a meal replacement approach that is also not scalable. Rejeski's study of patients with cardiovascular disease is the only example of a 'scalable' PA/dietary intervention for older adults of which we are aware. However, the scalability of the intervention is limited due to program length (weekly sessions for 6 months), and the use of a dietitian. Thus, the need for a scalable, efficacious PA/dietary intervention for the sizeable population of older adults with LE OA remains.*

*Eighty-five percent of participants in our effectiveness trial were overweight or obese at baseline, and many requested more help with diet and weight management than the curriculum currently offers. We propose to address this need by examining the feasibility, efficacy, and effectiveness of an intervention that combines an evidence-based PA program (Fit and Strong!) with elements of two evidence-based dietary programs (ADAPT and ORBIT). Several elements of the proposed study are highly innovative: 1) We will address a serious gap in the armamentarium of tools currently available to address the critical problem of obesity among older adults with LE OA. We will fill this gap by incorporating an evidence-based weight management protocol into the Fit and Strong! health education curriculum using intervention content and methods from both the ADAPT and ORBIT trials. Co-PI [name], recently completed the NCI-funded Obesity Reduction Black Intervention Trial (ORBIT) (CA105051). ORBIT tested the impact of a PA/diet intervention on obese middle-aged African American women. Using SCT and dietary change, ORBIT achieved a 5% reduction in weight at 6 months that was maintained at 18 months, very similar to the ADAPT findings ([name] et al., 2010). 2) The proposed PA/dietary intervention is scalable, and we have the experience and capacity to bring it to scale. We have demonstrated consistent benefits from Fit and Strong! across time, multiple geographic sites, instructors, and populations. The combination of this program with elements of effective dietary interventions in community-based settings has substantial potential to address the lack of scalable, efficacious PA/dietary interventions for older adults with OA. Further, our 8-week Fit and Strong! program benefits LE pain, stiffness and function using the same WOMAC and 6-minute distance walk measures used by ADAPT, but in half the time which is important for adoption purposes (Green & Glasgow, 2006). As the NIA Midwest Roybal Center for Health Promotion and Translation, we have the capacity to bring Fit and Strong! Plus to scale quickly if it demonstrates efficacy. We have developed instructor training protocols, an interactive website that tracks attendance and participant outcomes ([www.fitandstrong.org](http://www.fitandstrong.org)), Participant and Instructor Manuals, and standard procedures to monitor program fidelity in the field. We also have a Roybal Advisory Committee that includes representatives from several groups that are key to translation of EB programs, both locally and nationally (see Appendix A for Committee Roster). A recent review of 19 weight loss studies found that very few addressed issues of translation into real world settings and urged that future studies address how programs will be adopted and maintained with special attention to costs for participants and for program implementation (Akers, Estabrooks and Davy, 2010). 3) We now test the impact of dietary change as a route to weight loss out to 24 months in contrast to 18 month outcomes reported by current studies. 4) We will examine health care claims data and health-related quality of life pre and post both interventions. Fit and Strong! is currently being considered for inclusion in a Centers for Medicare and Medicaid Services (CMS) evaluation of appropriateness for Medicare reimbursement. The CMS data will enable us to examine impact of both programs on health care use and cost. 5) We will conduct the trial in local Park Department sites. Parks and Recreation*

[figure not shown]
sites are located all over the country and provide a systems delivery mechanism for taking Fit and Strong! Plus to scale. For all of these reasons, we believe we have reached an ideal time to test whether the already substantial impact of Fit and Strong! can be modified to achieve even greater improvements among persons with OA by also addressing weight management needs that are so common in this population.

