**Randomization**—After obtaining informed consent, participants will be assigned to Fit and Strong! or Fit and Strong! Plus using a randomized block design with blocks consisting of approximately 17 participants at each of the 3 sites. Within each block we will stratify by American College of Rheumatology (ACR) functional classes (I, II, or III) to achieve balance on arthritis severity by group. The random permutation of block sizes will help to minimize manipulation of an assignment.

**Inclusion/Exclusion Criteria**—*Inclusion criteria* include LE OA (hips, knees, ankles, feet, lower back), age 60+, no current participation in a regular exercise program, a calculated BMI of  $>=25 - 50 \text{ kg/m}^2$  (upper limit used in ORBIT) ([name] et al., 2010) and willingness to participate in measurement and intervention procedures. The study rheumatologist will examine participants at the baseline interview to confirm presence of LE OA and determine ACR functional class. *Exclusion criteria* include severe cardiovascular disease, active thrombophlebitis, recent pulmonary embolus, an acute systemic illness, poorly controlled diabetes, other health conditions that might preclude exercise training, age  $<60$ , current participation in organized PA, uncomplicated hip or knee surgery within the previous 6 months or complicated surgery within the past year, steroid injections in either knee or hip within the previous three months, or diagnosis of rheumatoid arthritis. Participants with blood pressure readings 180/110 mm Hg or higher or 90/50 mm Hg or lower will be excluded.

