Blood Pressure	
 
Blood pressure will be assessed using the NHANES protocol.
 

C. Independent Variables	
Demographic variables	
 
Age, race/ethnicity, sex, income, marital status, living arrangements, employment status, type of health insurance coverage, and education
 

Chronic Conditions	
 
Witham and Avenell (2010) recommend that future diet trials with older adults assess presence of co-morbid conditions
 
Will use index of co-morbid conditions used in GeriAIMS study ([name] et al., 1991)
 
Inquires about presence of 14 separate conditions and measures extent to which each condition interferes with activities
 

**Exploratory Variables**—The following measures will explore longitudinal risk of seeking total joint replacement, health care utilization, health care costs, and quality of life and technology usage in this population prior to and following participation.

**Readiness for Joint Replacement Surgery.** We will create a measure that will assess 1) degree of interest in total hip and knee replacement surgery and 2) intent to use either procedure in the next 6 months. We will monitor movement on that measure over time.

**Health Care Utilization.** Participants will complete the Health Care Utilization Measure (Lorig et al., 1996). to report number of physician and ER visits, hospital stays, hospital days, surgeries, outpatient tests and procedures, and medications used. We will obtain permission from participants to use their Social Security numbers to request healthcare utilization data from the Centers for Medicare and Medicaid. We will obtain data encompassing hospital and outpatient use, conditions, and prescription drug use. Specifically, we will request the MedPAR ss/ls/snf, Beneficiary Summary File, the Beneficiary Annual Summary file, and the corresponding crosswalk files for calendar years **2011-2016**. Calendar year data will be converted to **36**-month periods that correspond to **12** months prior to and **-18** months following baseline for each participant. Drs. [name] and [name] have prior experience analyzing these data ([name] et al., 2000; [name] et al., 2003).

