where  $Y_{it}$  represents a particular outcome variable for person  $i$  at time  $t$ , *Plus* is a dummy variable for the Fit and Strong! Plus effect, relative to customary Fit and Strong!, *Plus\*Time* represents the interaction with time, *ARA* is a covariate,  $u_i$  is the random effect for person  $i$  and  $e_{it}$  is a person-time specific error term. The *Plus\*Time* interaction tells us whether the rate of change with respect to time is greater (or less) in the Plus condition compared to customary Fit and Strong!. As shown, the model is for a continuous outcome, but it can be estimated for a wide variety of outcome variables (e.g., logistic regression and ordered logistic regression models). Time can be represented in multiple ways in addition to the simple linear effect shown here. By including the square of time we can test whether the effects of time are non-linear, and by including properly coded dummy variables for discrete time, we can test more specific hypotheses regarding non-linear effects. A crucial assumption of such models is that the person-specific error term,  $u_i$ , is uncorrelated with the remaining variables, which is plausible given the randomized design. The model, as written, assumes an “exchangeable” correlation matrix among the errors. However that assumption can be relaxed by using simple auto-regressive or Toeplitz (banded) correlation structures. All analyses will be done using Stata.

Analyses of secondary outcomes will examine the magnitude of between and within group differences at all time points to determine whether the addition of a diet component to Fit and Strong! benefits these outcomes (as expected) or is neutral or harmful with respect to certain outcomes. Exploratory analyses will evaluate movement on the new readiness for total joint replacement measure, and will examine patterns and trends in healthcare utilization, healthcare cost, and quality of life between and within the two study groups.

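### Before-and-after claims cannot show each program's effect on use and cost, because the entry criteria remove hip and knee surgery and joint injections from part of the 12-month pre-baseline window

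*Combined protocol and SAP*

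**What the plan says.** Innovation item 4 describes the claims work as a before-and-after exercise: "We will examine health care claims data and health-related quality of life pre and post both interventions". It then states the purpose: "The CMS data will enable us to examine impact of both programs on health care use and cost". The same item mentions that Fit and Strong! is under consideration for a Medicare reimbursement evaluation.

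The Health Care Utilization paragraph under Exploratory Variables defines the claims periods as those "that correspond to 12 months prior to and -18 months following baseline for each participant", but calls them 36-month periods.

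Under Inclusion/Exclusion Criteria, the exclusions include "uncomplicated hip or knee surgery within the previous 6 months or complicated surgery within the past year" and "steroid injections in either knee or hip within the previous three months".

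The Data Analysis section has one between-participant factor, customary Fit and Strong! against Fit and Strong! Plus. Its exploratory analyses "will examine patterns and trends in healthcare utilization, healthcare cost, and quality of life between and within the two study groups". The text available describes no untreated or external comparison group, and no allowance for the entry criteria in the claims analysis.

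**The concern.** Randomisation here estimates one contrast, Plus minus customary. It says nothing about what either program does compared with no program. A statement about the impact of both programs on use and cost must therefore come from the change within each arm around baseline.

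That change is partly fixed by eligibility. A person with a recent joint operation or injection cannot enrol, so those events are missing by selection from part of the period before baseline. The same events count in full afterwards, and both arms would show a rise in them even if neither program did anything.

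These are not marginal events in this trial. The Significance section motivates the study partly by the volume and cost of joint replacement, and the exploratory measures include readiness for replacement surgery. If the within-arm figures reached a reimbursement discussion, a selection artefact could count against a useful program or hide a real saving.

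**Working it through.** The plan gives no effect size or precision for the claims analysis, so there is no stated figure to reproduce. The check asks what a within-arm comparison would show if the programs had no effect.

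**Inputs from the documents.** Pre-window 12 months, post-window 18 months; exclusion look-backs of 6 months (uncomplicated surgery), 12 months (complicated surgery) and 3 months (injections); 400 participants; an 8-week program.

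**Assumptions.** Look-backs end at baseline. Surgery occurs at a constant rate L per person-year. A share c of surgery is complicated (0 to 20%). Hip and knee surgery makes up a share s of post-baseline cost (5 to 20%). The documents give none of L, c or s.

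**1. Observable pre-baseline months**
- Uncomplicated surgery: 12 − 6 = 6
- Complicated surgery: 12 − 12 = 0
- Injections: 12 − 3 = 9

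**2. Apparent change in annualised rate.** The observed pre-baseline surgery rate is L × (6/12) × (1 − c) and the post-baseline rate is L. The ratio is 1 / [0.5 × (1 − c)].
- c = 0: 1/0.50 = 2.0
- c = 10%: 1/0.45 = 2.2
- c = 20%: 1/0.40 = 2.5

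For injections the ratio is 12/9 = 1.33.

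**3. Allowing for deferral.** The Attendance/Retention paragraph asks people who expect to miss more than three classes to wait for a later round, which would push planned surgery away from the weeks after baseline. If no surgery at all occurs in the first 2 of the 18 months, the ratios are multiplied by 16/18 and become 1.8, 2.0 and 2.2.

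**4. Counts.** With 400 people and c = 0, expected surgeries in the pre-baseline year are 400 × L × 0.5, against 400 × L per post-baseline year. For L of 1, 3 and 5 per 100 person-years this gives 2 against 4, 6 against 12, and 10 against 20. The claims sample could be below 400, because participants must permit use of their Social Security numbers.

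**5. Total cost, with nothing else changing.** The ratio is 1 / [1 − s + 0.5 × s × (1 − c)].
- s = 5%: 1/0.975 = 1.026 (c = 0) to 1/0.970 = 1.031 (c = 20%)
- s = 10%: 1/0.950 = 1.053 to 1/0.940 = 1.064
- s = 20%: 1/0.900 = 1.111 to 1/0.880 = 1.136

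The apparent rise is thus about 3% to 14%. With c = 0, a fall in all other cost of s × 0.5 / (1 − s) would cancel it: 2.6%, 5.6% and 12.5% for the three shares.

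**6. Like-for-like check.** Comparing uncomplicated surgery only, in months −12 to −6, with the annualised post-baseline rate of uncomplicated surgery gives an expected ratio of 1.0. This confirms that the apparent rise comes from the excluded months. The expected Plus minus customary difference is 0 under no effect, because both arms pass the same entry rules.

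**7. Window lengths.** 12 + 18 = 30, not 36. A 24-month follow-up, which the plan mentions elsewhere, would give 12 + 24 = 36 and leave step 2 unchanged. An 18-month pre-window would also give 36 (18 + 18). The ratio would then be 18/12 = 1.5 at c = 0, and 18 / (12 × 0.8 + 6 × 0.2) = 1.7 at c = 20%.

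**The case against.** The strongest reply is that this work is labelled exploratory, that the Data Analysis section already includes the between-arm comparison, and that the sentence about both programs is narrative in the Innovation section rather than an analysis specification. No passage says that a within-arm rise will be reported as program impact. All of this is correct, and it limits the weight of the point. It does not remove it: the narrative states the purpose of the claims data, within-arm trends are planned, and nothing warns that those trends are shaped by eligibility.

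A reader might infer more than the documents support:

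- **That total use and cost must appear to rise.** The upward direction is shown only for the excluded events. Total cost depends on an unstated share and on whatever else shifts after enrolment. A fall from a symptom peak at entry, for example, could offset the rise.
- **That surgery would triple.** Raw counts over 18 against 12 months do give 3-fold at c = 0, but 1.5 of that is unequal window length, which annualising removes.
- **That a dollar figure can be attached.** The Significance section implies $11 billion / (225,900 + 431,485), about $16,700 per procedure. That is a 2004 hospital cost for replacements, whereas the criteria exclude hip or knee surgery in general.
- **That every health exclusion contributes a known amount.** The list "severe cardiovascular disease, active thrombophlebitis, recent pulmonary embolus, an acute systemic illness, poorly controlled diabetes" gives no look-back lengths. These criteria probably act in the same direction, but their effect on the window cannot be calculated.

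**Conclusion.** The point holds for the within-arm reading of claims. Under a constant rate, no program effect and the stated 12-month pre-window, hip and knee surgery would appear to rise about 2-fold per year. The range is 2.0 to 2.5 across the assumed complicated shares, or 1.8 to 2.2 if surgery is absent for the first 2 months after baseline. Injections would appear to rise about 1.33-fold.

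For total use and cost, neither the direction nor the size can be established from the documents. The 3% to 14% range is illustrative and assumes that nothing else changes. An offset of unknown size does not rescue the within-arm total; it leaves it uninterpretable as the impact of either program.

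The randomised Plus versus customary comparison is unbiased in this respect, and the primary outcomes are untouched. This is a change the plan should make, not a threat to the trial's main conclusions. Some of the Approach section was not available, so any wording there on the aims of the claims work could not be checked.

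**What to change.** In Innovation item 4, the Health Care Utilization paragraph and the Data Analysis section:

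1. Define the use and cost effect as the between-arm difference, Plus minus customary, in post-baseline use and cost per person-month, adjusted for the pre-baseline value. The entry criteria shape that covariate equally in both arms, so the adjustment does not bring the problem back.
2. Withdraw the statement that before-and-after claims show the impact of each program.
3. Label within-arm before-and-after tables descriptive, express both windows per year, and leave hip and knee surgery out of both. Do the same for joint injections where the files identify them.
4. Reconcile the 36-month span with the 12 months before and 18 months after baseline.

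The cost is wording only: the data files and participant burden stay the same. The trial gives up a claim about each program's own effect on cost, which two active arms and this pre-baseline window cannot support.
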